### 1.5 Community-acquired pneumonia and S. pneumoniae

In adults, 60-80% of community-acquired pneumonia (CAP) cases are caused by bacteria; rates of infection are highest in those aged  $\geq$  65 years. *S. pneumoniae* is the most common cause of bacterial pneumonia in adults and the elderly. The attack rate of CAP is influenced by the seasonal pattern of viruses predisposing to pneumonia. In Leicester, weekly admissions data for the 1352 cases of CAP admitted during the winters of 2002/3 and 2003/4 shows two peaks of 5 and 6 weeks duration during 2002/3 and a 14-week peak during 2003/4, suggesting a possible relationship with respiratory virus activity. Between 9.5% - 48% of CAP may involve coinfection of typical and atypical organisms. Of the 148 cases of *S. pneumoniae* identified by Porath *et al*, 100 had co-pathogens identified, usually 'atypicals'. Although the clinical importance of polymicrobial infection is uncertain, mixed infection may be associated with a more complicated course. The mortality from pneumococcal pneumonia in hospitals is ~2.5%. Treatment cannot await the results of conventional microbiological tests, so an empiric regimen is necessary, which in the UK typically includes a  $\beta$ -lactam antibiotic, with or without a macrolide.

It is possible that patients with a positive rapid pneumococcal antigen test result may receive a single antimicrobial agent, and that mortality of patients with polymicrobial infection including S. pneumoniae is increased. Oosterheert *et al* recently undertook a systematic review to assess whether treatment with a  $\beta$ lactam plus macrolide or quinolone monotherapy is truly superior to beta-lactam treatment alone. Eight relevant studies were selected. In six, significant reductions in mortality were found; in one, a reduction in hospital length of stay was found; and in another no beneficial effects could be demonstrated for treatment regimens with fluoroquinolone monotherapy or combinations of  $\beta$  -lactams and macrolides. The studies supporting the recommended treatment regimen were designed as non-experimental cohort studies. As a consequence, confounding may have influenced the results. In addition, the outcomes showed several inconsistencies. The authors concluded that a randomised controlled trial is warranted to circumvent the methodological flaws in the designs of the currently available studies, particularly as the addition of macrolides or treatment with fluoroquinolones may lead to enhanced antibiotic resistance, increased side effects, and healthcare-related costs. In Leicester, the recommended empiric therapy for patients hospitalised with CAP consists of monotherapy with a β-lactam agent or erythromycin if allergic to penicillin. Addition of a macrolide is not recommended unless the pneumonia is severe and therapy is adjusted 'as appropriate' at 48 hours if there has been no improvement. Although the available evidence does not indicate that rapid near patient pneumococcal antigen testing will adversely affect patient outcome, we plan that an independent Data Monitoring Committee conduct interim analyses to ensure that patient welfare is not adversely affected.

#### **1.6** Diagnostic tests for influenza

Viral isolation and haemagglutination inhibition antibody testing are standard methods for influenza diagnosis, but have drawbacks. Virus isolation by culture from respiratory secretions may take a week or

more (a median of 8 days in one recent study); it requires specialised laboratory facilities; and does not provide results that could influence the initiation of treatment. Serology provides a retrospective diagnosis. Neither test alone is considered a 'gold standard' for influenza diagnosis, since each lacks sensitivity, but culture and serology together have been used as 'gold standard' to assess molecular diagnosis.

Tests for rapid diagnosis of influenza A and B virus by immunofluorescence of exfoliated nasopharyngeal cells have shown variable sensitivity (40 to 100%) and specificity (86 to 99%); they require specialist equipment and expertise and are labour intensive. Rapid, near-patient tests for influenza vary in complexity, sensitivity, and specificity. They can aid clinical management, but their value in the hospital setting in influencing prescribing and infection control is unclear. We plan to use the Quidel QuickVue influenza A and B test. It is the most rapid of the near patient tests; is particularly simple to perform; and has a median sensitivity and specificity of 80%. Its diagnostic accuracy in the elderly is unknown. Molecular diagnosis of influenza by reverse transcription PCR (RT-PCR) provides improved sensitivity and specificity, allows accurate detection, and facilitates the subtyping of influenza. Multiplex PCR has the added advantage of allowing identification of several infectious agents (e.g., influenza subtypes A/H1N1, A/H3N2, and B, and RSV types A and B) in one sample and in one reaction. The technique is used routinely within the specialist diagnostic facilities of the Health Protection Agency, Colindale, where it has a sensitivity of 92% and specificity of 84%. We plan to evaluate the ease of use and usefulness of PCR in Leicester as part of the process of distributing it more widely.

#### 1.7 Diagnostic tests for RSV

Factors contributing to underestimations of the incidence and burden of RSV in the elderly include virus lability; the brief period of virus shedding and low titre of virus in nasal specimens during reinfection; the relative insensitivity of standard diagnostic tests – including the complement fixation test (CFT), virus culture (even when performed under rigorous conditions including bedside inoculation), and rapid antigen detection tests (immunofluorescence and Directigen enzyme immunoassay) in the elderly; and the frequent co-circulation of RSV with influenza. Multiplex reverse-transcriptase polymerase chain reaction (RT-PCR) has emerged as a sensitive and specific method of detecting RSV infection. Examination of nose and throat swabs by multiplex RT-PCR from 167 elderly subjects (age  $\geq$ 65 years) who presented to their general medical practitioner with influenza-like illness during the winters 1995/6, 1996/7, and 1997/8 showed that 15% had RSV. These investigators detected one RSV infection for every two influenza infections, suggesting that the previously unrecognised burden of RSV in the elderly may be substantial.

#### 1.8 Diagnostic tests pneumococcal pneumonia

Diagnosis of pneumococcal pneumonia is complicated by the lack of a diagnostic reference standard that is highly sensitive and specific. Despite being the single most important pathogen causing CAP, *S pneumoniae* is undoubtedly underdiagnosed due to limitations of conventional tests. Limitations of Gram stain and culture of sputum include failure to obtain a sputum sample – only a minority of patients are able to produce sputum samples; the overall diagnostic yield of sputum examination is very low (<25%); and isolation of *S pneumoniae* from sputum may represent colonisation. Historically, blood cultures were considered a standard of care for the investigation of patients with CAP. Positive blood culture results are found in <10%

of patients with CAP. The test is rarely useful, as positivity becomes evident no earlier than 24h after obtaining the specimen, and results typically have little influence on therapeutic decisions and outcomes. However, a review of patients with confirmed pneumococcal pneumonia, found that 42% of patients with positive blood culture results had their treatment changed as a result. Since the overall prevalence of  $\beta$ -lactam resistance remains low in the UK, rapid near patient testing for pneumococcal infection could influence therapeutic decisions.

Measurement of pneumococcal antibodies has not proven reliable for diagnosing pneumococcal pneumonia. PCR appears to be more sensitive than blood culture, but most studies have tested only a small number of samples, and have not compared different sample types from the same patients (see Murdoch *et al*). Murdoch *et al* used a nested PCR to target the pneumolysin gene in multiple sample types from 474 adults with CAP. The authors conclude that the pneumolysin PCR adds little to existing diagnostic tests and that it was less sensitive than the rapid urine antigen test. The detection of *S pneumoniae* antigens in the urine of patients with pneumonia has been extensively studied using a variety of techniques. While the performance of most tests has been disappointing, the Binax NOW urinary antigen test that we will use is simple to perform; it can detect the C polysaccharide cell wall antigen common to all *S pneumoniae strains*; and it provides results within 15 min. It has a sensitivity of 80% or more in adults and children, when positive blood cultures are used as the 'gold standard'.

#### 1.9 Clinical and cost-effectiveness of rapid diagnosis

Few studies have examined the impact of rapid diagnostic tests for influenza, RSV and *S. pneumoniae* on patient management, clinical outcomes, and cost-effectiveness. Potentially, the benefits might include: (i) improved infection control; (ii) more efficient use of antiviral therapy and (iii) more efficient use of antibiotics.

Several retrospective observational analyses have been done on the effectiveness of rapid tests for various respiratory virus infections in children. Woo *et al*  observed a mean reduction in hospital stay of 1.3 days (P<0.001) following the introduction of rapid diagnosis. There were significant reductions in the duration of antibiotic use (52% reduction) and number of other microbiological investigations performed, and the cost of implementing the programme was more than offset by a reduction in the mean duration of stay. Barenfanger *et al* found non-significant reductions in mortality and length of stay in the hospital following the introduction of rapid diagnosis. Byington *et al* noted a significant decrease in inappropriate antibiotic use.

A retrospective observational study, and a randomised controlled trial (RCT), evaluated rapid near patient diagnostic tests for influenza in children's hospitals. The observational study showed that patients with a positive near-patient test were as likely to receive antibiotics as culture-confirmed cases, but the duration of antibiotic treatment was two days shorter. Patients with a positive diagnosis were also more likely to receive antibiotics prescribed; (iii) use of antivirals, and (iv) the length of stay in the emergency department when the diagnosis of influenza was apparent at the time of assessment.

Cost-benefit analyses of near patient influenza testing have focused on its role in guiding treatment with neuraminidase inhibitors rather than the more efficient use of antibiotics or shorter duration of stay in hospitals. No studies of the clinical and cost-effectiveness of rapid molecular testing for RSV have been carried out to our knowledge. Oosterheert *et al* developed an algorithm to assess the potential costs and savings associated with the use of rapid diagnostic testing for pneumococcal pneumonia and evaluated the cost savings for 122 consecutively admitted patients with CAP. They identified no cost-reductions, which they ascribed to the small proportion of patients who could provide sputum, the small proportion of patients with CAP in their study who had pneumococcal pneumonia, and the small price difference between narrow-spectrum and broad spectrum therapy.

#### 1.10 The EuroQol Instrument

The EuroQol instrument assesses quality of life by means of 5 questions with three possible answers to each question and produces valuations on a scale which has fixed points of 1 (full health) and 0 (death). It has been widely used in economic evaluations of health care interventions. The EuroQol can be used to generate the outcome of 'Quality Adjusted Life Years' (QALYs) where quality of life in any health state is combined by the duration of that health state. Three different versions of the EuroQol instrument are available. These are a patient self-complete form, a form for completion by interview, and a proxy form (Appendix I).

#### **1.11** Rationale for the study

Rapid near patient testing for influenza and pneumococcal infection, and rapid molecular tests for influenza and RSV will be justified if, as expected from existing knowledge, it can be shown that:

- Influenza, RSV, & *S. pneumoniae* infections occur as frequently as expected in the target population in the UK, & have an important impact on morbidity, mortality and quality of life.
- Rapid near patient and molecular tests are as reliably sensitive and specific in elderly patients admitted to a UK hospital as they are in other populations and settings; they are as easy to use as expected; and they provide clinically useful data to clinicians as rapidly as expected.
- Rapid diagnostic tests improve the opportunities for infection control in hospitals as expected by reliably identifying patients who, unless isolated, may transmit influenza or RSV to vulnerable patients and staff.
- Rapid diagnostic tests prevent or minimise unnecessary use of antibiotics in patients with viral infections.
- Rapid diagnostic tests aid therapeutic decisions in patients with CAP.
- Rapid diagnostic tests are not associated with increased morbidity or mortality in patients whose treatment would have been different without knowledge of the pathogen.

The selected study population is a key component of the recurrent bed crises experienced by the NHS in winter. Ironically, specific infective diagnoses are rarely obtained in these patients. This reflects the widespread perception that conventional test results are of dubious value, are usually available too late and that empirical therapy offers the best approach to management. As a result, very few centres have a clear view of the major pathogens responsible or have policies that take such information into account. Nonetheless, such information could and should have a profound influence on 1) antibiotic and antiviral use,

2) patient isolation and nursing policies, and 3) policies for immunisation of staff and the local community. Moreover, the timely provision of results through technologies to be assessed could transform attitudes to the value and applicability of results. Thus, while technology assessment is the primary driver and will be decisively achieved by our design, we contend that our proposal embodies exceptional added value by providing essential epidemiological data relating to a major burden on the NHS.

In this study, we will gather core information concerning the contribution of three key pathogens to winter admissions, validate rapid tests in two settings, and determine the effects of providing results on patient outcomes and management. We emphasize that, if the tests prove valid in this setting, our results will provide a major resource enabling improved planning in response to the winter burden of cardio-respiratory admissions in many different communities.

#### **2 OBJECTIVES OF THE STUDY**

#### 2.1 Research objectives and hypotheses

In the Medical Admissions Units/Wards of the University Hospitals of Leicester, to:

1. Determine the diagnostic accuracy (sensitivity, specificity, positive and negative predictive values) of rapid molecular and near patient diagnostic tests for influenza, RSV and *S. pneumoniae* infections in comparison to traditional laboratory culture.

The increased diagnostic accuracy of rapid molecular and near patient tests over traditional laboratory methods improves patient management through better use of antimicrobials and isolation facilities. Rapid molecular and near patient diagnostic tests for influenza, RSV and S. pneumoniae infections are more cost-effective than traditional laboratory diagnostic tests.

2. Assess the potential benefits of ease of use, and speed of rapid molecular and near patient diagnostic tests for influenza, RSV and *S. pneumoniae* infections, in comparison to traditional laboratory culture.

Rapid molecular and near patient diagnostic tests for influenza, RSV and S. pneumoniae infections provide benefits in terms of (a) ease of use, and (b) more rapid results, in comparison to traditional laboratory culture.

3. Determine whether rapid molecular and near patient diagnostic tests for influenza, RSV and *S. pneumoniae* infections have any impact on prescribing.

Rapid molecular and near patient diagnostic tests for influenza, RSV and S. pneumoniae infections result in earlier use of narrow-spectrum antimicrobial therapy; and/or an earlier switch from intravenous to oral therapy; and/or earlier discontinuation of antibiotics in patients infected with influenza and RSV - in comparison to traditional laboratory culture

4. Determine whether rapid molecular and near patient diagnostic tests for influenza, RSV and *S. pneumoniae* infections allow more appropriate use of isolation facilities, in comparison to traditional laboratory culture.

Rapid detection of influenza and RSV by rapid molecular and near patient diagnostic tests leads to the appropriate isolation of patients, but only in hospitals/wards with an adequate provision of cubicles.

5. Compare the costs of performing rapid molecular and near patient diagnostic tests for influenza, RSV and *S. pneumoniae* infections, in comparison to traditional laboratory culture.

The costs of performing rapid molecular and near patient diagnostic tests for influenza, RSV and S. pneumoniae infections, differ significantly from the cost of traditional laboratory culture.

6. Assess cost-savings associated with earlier use of narrow-spectrum antimicrobial therapy (or avoidance or discontinuation of antibiotics) in patients whose influenza, RSV and *S. pneumoniae* infections are diagnosed more rapidly by rapid molecular and near patient diagnostic tests, in comparison to traditional laboratory culture.

The earlier use of narrow-spectrum antimicrobial therapy (or avoidance or discontinuation of antibiotics) in patients whose influenza, RSV and S. pneumoniae infections are diagnosed more rapidly by rapid molecular and near patient diagnostic tests results in significant cost-savings, in comparison to traditional laboratory culture.

7. Compare the outcome of patients whose influenza, RSV, and *S. pneumoniae* is diagnosed more rapidly by rapid molecular and near patient diagnostic tests, compared to those who are diagnosed by traditional laboratory culture.

A streamlining of antimicrobial prescribing that may arise from more rapid diagnosis of influenza, RSV and S. pneumoniae infections by rapid molecular and near patient diagnostic tests does not adversely affect patient outcome.

8. Assess the impact that rapid molecular and near patient diagnostic tests have on the costs associated with an inpatient stay and on costs post-discharge up to a maximum of 28 days after admission.

Any increase in costs incurred by rapid molecular and near patient diagnostic tests, in comparison to traditional laboratory culture, is more than offset by savings that arise from either rational antimicrobial prescribing or earlier discharge from the hospital.

9. To assess the impact that rapid molecular and near patient diagnostic tests have on quality-of-life, as measured by the EuroQol (Appendix I), and to use this information to estimate the quality adjusted life years (QALYs) generated during the 28 days after admission.

Rapid molecular and near patient diagnostic tests result in an improvement in quality-of-life, as measured by the EuroQol, which arises from streamlining of antibiotics and earlier discharge into the community.

10. To assess the cost-effectiveness of rapid molecular and near patient diagnostic tests in comparison to the cost/QALY of cases diagnosed correctly by traditional laboratory culture. To assess the costeffectiveness of rapid molecular and near patient diagnostic tests in comparison to traditional laboratory culture. This will be done on the basis of both cost per case detected and cost per QALY.

Rapid molecular and near patient diagnostic tests are more cost-effective than traditional laboratory culture.

11. To explore whether patients with pneumococcal infection have lower levels of cellular and humoral immunity to the pneumococcus in comparison to patients who do not have pneumococcal infection.

Patients with pneumococcal infection have lower levels of cellular and humoral immunity to the Pneumococcus in comparison to patients who do not have pneumococcal infection.

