### ANALYSIS

The sample size is based on the admissions during 2002-03 and 2003-04 (September 1 – April 30) for elderly ( $\geq$ 65 years old) patients with acute cardio-pulmonary conditions, excluding angina and myocardial infarction. There were 2762 acute cardio-pulmonary admissions during September 1 – April 30 2002-03, and 2852 during 2003-04, i.e., an average of 11.57 admissions ( $\geq$ 65 years) per day.

The study will run for at 666 days (242 during each of Years 1 and 2, and 183 during Year 3), i.e., the number of eligible patients is estimated at 666x11.57=7705.6. We plan to recruit 5 days per week, which reduces the eligible number of patients to  $(5\div7)x7705.6=5504$ . We understand that two-thirds are admitted during the period 09:00-21:00h, which reduces the evaluable pool to 3669. We estimate that three-quarters of eligible subjects will participate, i.e., we expect to recruit 2752 elderly ( $\geq 65$  years old) patients with acute cardio-pulmonary conditions. Of these, 664 are expected to have ICD codes for pneumonia; 556 are expected to have exacerbations of chronic obstructive pulmonary disease; and 735 are expected to be admitted with heart failure.

We estimated the number of admissions in 'high-risk' 18-64 year-olds by extrapolation using (i) national cardio-pulmonary hospital admission data for patients aged 15-59 years, 60-74 years, and 75 years and older and (ii) the number of cardio-pulmonary admissions aged  $\geq$ 65 years in Leicester.

	We assumed that half of the patients admitted with pneumonia, unspecified lower respiratory tract infections, and exacerbations of COPD have underlying high-risk conditions. We expect to recruit 83 18-64-year old patients with pneumonia, 93 with unspecified lower respiratory tract infections, and 181 with COPD. These have not been included in the following estimates: On the basis of historical data we expect that one-third of elderly patients with pneumonia have pneumococcal disease (i.e., 221) but expect the
	number identified by the pneumococcal antigen test to be higher. Of the 221, ~73 should be randomly allocated to the rapid near patient test (Binax NOW) (Group 1); the remainder will be randomised to the group tested by traditional methods (Groups 2 & 3). However, as identical sample sets will be taken from each individual, diagnostic accuracy will be assessed in a minimum of 221 subjects.

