- Based on the above, we expect to recruit 747 participants with pneumonia, of whom at least one third (n=249) should have *S. pneumoniae* infection. Of these, ~83 should be randomly allocated to the rapid near patient test (Binax NOW); the remainder will be randomised to the group tested by traditional methods. Thus the speed of diagnosis, impact of early diagnosis on prescribing, clinical outcomes, and costs will be assessed in groups having an estimated 83 and 166 subjects. However, as identical sample sets will be taken from each participant, the diagnostic accuracy of the tests will be assessed in all 249 subjects. The number of cases of *S. pneumonaie* infection that are likely to be identified among the anticipated 649 (556 +93) participants with unspecified acute lower respiratory tract infections is unknown, but their occurrence will add to the pool of cases for studies of diagnostic accuracy.
- On the basis of the Rochester study, we expect that 10% of the 2752 elderly (≥65 years) participants will have influenza A or B. Of the 275, one third (~92) will be allocated to the QuickView near patient influenza immunoassay; one third will be allocated to the rapid molecular group; the remainder will be allocated to the group tested by traditional methods. Identical sample sets will be taken from each individual, so the diagnostic accuracy of the tests will be assessed in all 275 subjects.
- Similarly, we expect that 5% of the 2752 elderly (≥65 years) participants will have RSV A or B. Of the 138, one third (~46) will be allocated to the rapid molecular group; the remainder (~92) will be allocated to the group tested by traditional methods. We expect that very few of these will be found

positive by the routine tests employed. Identical sample sets will be taken from each individual, so the diagnostic accuracy of the tests will be assessed in all 138 subjects.

While the numbers of patients with influenza and RSV who are allocated to the 'rapid' near patient or molecular tests are comparatively small (~92 + ~46 per elderly group, plus cases occurring in the 18-64-year-olds), the impact of a 'viral' infection (RSV or influenza) infection on patient isolation, antimicrobial prescribing, and clinical outcomes may be compared using a larger combined group – i.e.,

Elderly

Rapid influenza & RSV (i.e., Quickview + molecular tests) n=(92+92+46)=230Traditional influenza & RSV n=(92+46+46)=184

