  First, the proportion of patients with *S. pneumoniae* infection in Groups 1, 2, and 3.
  Second, to better define the burden of influenza and RSV, the proportion of all patients with (i) influenza, and (ii) RSV, who die.
- 3. Quality of life, as measured by EuroQol, and quality adjusted life years generated during the 28 days after admission, will be assessed:
  - (a) In all patients in Groups 1, and 2 in comparison to Group 3.

- (b) Second, in patients in patients with (i) influenza, (ii) RSV, and (iii) *S. pneumoniae* in Groups 1, and 2, in comparison to Group 3.
- 4. Use of isolation facilities
  - (a) The time from admission to the MAU to the time of admission to a single room (isolation cubicle) will be compared for patients with confirmed influenza or RSV in Groups 1, 2, and 3.
  - (b) The proportion of patients with influenza or RSV in Groups 1, 2, and 3 who are isolated at any stage during the first 120 hours of the admission.
  - (c) The proportion of patients with *S. pneumoniae* infection in Groups 1, 2, and 3 who are inappropriately isolated for >12 hours.

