#### 7.6 Statistical analysis

All analyses for both process and clinical outcomes will be based on Intention to Treat (ITT) analyses.

Impact of test result on prescribing The time to prescription of `narrow spectrum', `oral antibiotics' or `no antibiotics' between the three groups will be assessed using survival analysis techniques, whilst the use of neuraminidase inhibitors in those with influenza will be assessed using  $\chi^2$  tests, together with 95% CIs. Further analyses to allow for potential differences in patient demographics and baseline clinical characteristics between the three diagnostic test groups, and not allowed by stratification, will make use of cox proportional hazards regression modelling in the case of time to appropriate prescribing and logistic regression techniques in the case of neuraminidase inhibitors.

*Length of hospital stay* Length of hospital stay in the three diagnostic groups will initially be compared using non-parametric methods. Further analyses to allow for potential differences in patient demographics and baseline clinical characteristics between the three diagnostic test groups, and not allowed by stratification, will make use of generalised linear models in order to accommodate any skewness in the data.

*Mortality rates* Mortality rates between the three diagnostic testing groups will be compared by means of a Log-Rank Test and Kaplan-Meier survival curves. Adjustment for potential differences in patient demographics and baseline clinical characteristics between the three diagnostic test groups, and not allowed by stratification, will make use of Cox proportional hazards regression methods.

*Diagnostic accuracy* Sensitivity, specificity, positive predictive value of molecular and near patient diagnostic tests in comparison to traditional laboratory methods will be calculated together with 95% CIs. Heterogeneity in the sensitivity and specificity with respect to patient demographics and baseline clinical characteristics will be explored as secondary analyses using patient defined sub-groups.

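### Hypothesis 7 claims no harm, but death, intensive care and ventilation get only difference tests without a margin, and sections 7.5.1 and 7.6 disagree on who is compared

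*Protocol*

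**What the plan says.** Objective 7 (Protocol, section 2.1) compares outcome in patients whose influenza, RSV or S. pneumoniae infection is diagnosed faster with outcome in those diagnosed by culture. Its hypothesis is that the resulting streamlining of antimicrobials "by rapid molecular and near patient diagnostic tests does not adversely affect patient outcome". Section 1.11 makes the same point a condition for justifying the tests: "Rapid diagnostic tests are not associated with increased morbidity or mortality" in patients whose treatment would otherwise have been different.

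The analyses are in section 7.6. For death: "Mortality rates between the three diagnostic testing groups will be compared by means of a Log-Rank Test and Kaplan-Meier survival curves", with Cox regression for adjustment. For intensive care and ventilation: chi-squared tests with 95% confidence intervals, then logistic regression. No margin appears anywhere. Section 7.4 gives power for diagnostic accuracy, length of stay and isolation only.

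The populations differ between sections:
- Section 7.5.1, items 2(d) to 2(f), lists intensive care, ventilation and death by group in S. pneumoniae cases. The viral cases enter separately, "to better define the burden of influenza and RSV, the proportion of all patients with (i) influenza, and (ii) RSV, who die", with no split by group. Items 2(a) to 2(c) begin with all patients.
- Section 7.6 compares the three groups without restriction, under intention to treat.
- The synopsis (Assessment methods, Clinical outcomes) compares deaths in Groups 1 and 2 with Group 3, also without restriction.
- The end of section 7.3 says evaluations use both confirmed cases and everyone investigated under each strategy.

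**The concern.** A test for a difference cannot establish that there is none. If few deaths are expected, the log-rank test will usually be non-significant whether or not the rapid tests do harm, and without a margin or an interval for mortality the report has nothing firmer to rest on.

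The choice of population matters as much. Sections 1.5, 3.5 and 10.4 name the hazard: a pneumococcal patient with polymicrobial infection whose therapy is narrowed on a rapid result. That harm would arise in the smallest comparison. Objective 7 also covers influenza and RSV, where endpoint 1(c) looks for antibiotics being stopped, yet 7.5.1 lists no by-group comparison of death, intensive care or ventilation for those patients. With 7.5.1 and 7.6 unreconciled, an analyst could choose the population that answers hypothesis 7 after seeing the results.

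**Working it through.** **Inputs from the protocol.**
- Control mortality: "The mortality from pneumococcal pneumonia in hospitals is ~2.5" per cent (section 1.5), the only rate given.
- Elderly pneumococcal cases: 221, a third of 664 (synopsis, Sample size). With 18 to 64-year-olds: 249 (section 7.1).
- Total elderly recruited: 2752.
- Dropout: 20%, stated in section 7.4 for other endpoints and applied here as an assumption.

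**Assumptions.** Equal thirds; two-sided 5% level for each pairwise comparison.

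**Reproducing the counts.** 664/3 = 221.3, and 221.3/3 = 73.8; the synopsis says "Of the 221, ~73 should be randomly allocated to the rapid near patient test (Binax NOW) (Group 1"). 249/3 = 83, as in section 7.1. After dropout, 221 × 0.8/3 = 59. For all patients, 2752/3 = 917, and 2752 × 0.8/3 = 734. The protocol states no power for mortality, so there is no such figure to reproduce.

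**Pneumococcal cases.** With 74 per group, expected deaths are 74 × 0.025 = 1.9 against 74 × 0.05 = 3.7 for a doubling. The normal approximation is

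power = Φ{[|p₂ − p₁|√n − 1.96√(2p̄(1 − p̄))] / √(p₁(1 − p₁) + p₂(1 − p₂))}.

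For 2.5% v 5%, n = 74: (0.2151 − 0.5266)/0.2681 = −1.16, so power is 12.3%. With so few events, exact enumeration of the chi-squared test, counting only results in the direction of harm, is safer:

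| n per group | 2.5% v 5%: power | missed | 10% v 20% (assumed): power | missed |
|---|---|---|---|---|
| 59 | 8.8% | 91% | 33.6% | 66% |
| 74 | 11.0% | 89% | 40.5% | 60% |
| 83 | 11.3% | 89% | 43.9% | 56% |

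The Schoenfeld approximation for the log-rank test at 74 per group gives 13.0%. By the normal approximation, 80% power for this doubling needs 906 per group.

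**Precision.** The 95% half-width for a difference with 2.5% in both groups is 1.96√(2 × 0.025 × 0.975/n): 5.0 points at n = 74, 5.6 at 59 and 4.8 at 83. That is about twice the baseline rate.

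**All randomised patients.** The protocol gives no all-patient mortality, so 2.5% is assumed, with 5% as a second value. Exact power, same test:

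| n per group | 2.5% v 5% | 2.5% v 3.75% | 5% v 10% | 5% v 7.5% |
|---|---|---|---|---|
| 734 | 72% | 28% | 96% | 51% |
| 917 | 81% | 34% | 98% | 60% |

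The half-width at 2.5% is 1.4 points (917) or 1.6 points (734).

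**Harm confined to pneumococcal cases.** They are 221/2752 = 8.0% of patients. A doubling from 2.5% adds 2.5 points in that 8.0%, or 0.080 × 2.5 = 0.2 points overall, well inside the all-patient half-width of 1.4 points.

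**The case against.** Four objections carry weight.

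1. A reader might infer that the trial has no all-patient comparison of death. The documents do not support that: the synopsis, section 7.3 and section 7.6 all plan one, and its power for a doubling is reasonable. What stands is that 7.5.1 lists these three outcomes differently.
2. A reader might infer that no interval is planned for any safety outcome. Section 7.6 promises 95% intervals for intensive care and ventilation; only mortality lacks a stated one. Other outcomes are compared by group more widely: length of stay, fever, oxygen dependence and EuroQol in all patients, and length of stay and EuroQol also in each of the three infections.
3. The statement that hypothesis 7 would be accepted from a non-significant result is an inference. No decision rule is written, it is one of eleven hypotheses, and an unseen analysis plan may deal with interpretation. But the protocol itself fixes the hypothesis, the tests and the endpoint populations, and these do not fit together.
4. The pneumococcal inputs are on the low side. The synopsis expects antigen testing to find more than 221 cases, section 7.1 adds younger patients and an unknown number from other lower respiratory infections, and 2.5% is a general hospital figure. At an assumed 10% the miss rate falls to 56 to 66%, which is still far from adequate.

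Monitoring by the independent committee does not supply the missing criterion. Section 10.4 is a reporting trigger during the trial, not a rule for the final conclusion.

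**Conclusion.** The point holds as a should-fix. A no-harm claim is paired with difference tests and no margin, so non-significance is the most the stated plan can offer for death, and the sections disagree about which patients are compared.

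In pneumococcal cases a doubling of mortality from the protocol's 2.5% is missed about 89 to 91% of the time, with an interval of about ±5 points. This rests on 59 to 83 per group and a two-sided 5% test. The all-patient comparison is much stronger for a doubling (81%, or 72% after dropout, from an assumed 2.5%) but weak for a 1.5-fold rise (34%, or 28%).

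Two stronger readings should be resisted. It is not shown that the trial is bound to declare safety: the all-patient analysis could detect a doubling across the board. Nor would an all-patient margin alone settle the matter, because a doubling confined to pneumococcal cases shifts the overall rate by only about 0.2 points.

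**What to change.** 1. In section 7.5.1, items 2(d) to 2(f), and the matching synopsis text, list the comparison of death, intensive care admission and ventilation in all randomised patients (Group 1 v 3, Group 2 v 3). Then list by-group results for S. pneumoniae, influenza and RSV cases. The pooled burden figures can stay.
2. In section 7.6, add an effect estimate with a 95% confidence interval for mortality, as already promised for intensive care and ventilation.
3. In section 7.6, state that hypothesis 7 will be judged on the upper confidence limits, shown for all patients and for the pneumococcal subset, against a margin that the Trial Steering Committee fixes before it sees outcome data by group. State also that non-significance is not evidence of safety, and that an all-patient bound alone does not exclude harm in pneumococcal cases. The timing is best tied to sight of outcome data by group rather than to unblinding, because clinicians receive results by group and section 10.4 has the Principal Investigator told the study group of each death.

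The cost is wording, plus the committee's work in setting a margin; the data are already collected. The downside is that the trial may have to report that harm was not excluded, which is likely in the pneumococcal subset unless the margin is wide.
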